7.6.2 Laboratory Values

Clinical laboratory values will be summarized by visit and by treatment group using descriptive statistics for hematology, chemistry, and urinalysis. For quantitative laboratory parameters, both actual values and change from Baseline values will be summarized.

Laboratory test results will be assigned a low, normal, high (LNH) classification according to whether the values were below (L), within (N), or above (H) the laboratory parameters' reference ranges provided by the central laboratory. Within-treatment comparisons will be based on 3 x 3 tables (shift tables) that, for a particular laboratory test, compare the LNH classification at baseline to the LNH classification at visit. Listings of all abnormal laboratory values by subject (i.e., those with L or H classification) will be provided.

7.6.3 Vital Signs, Height, Weight, and BMI

Vital signs will be summarized by the visit and by treatment group using descriptive statistics. Both actual values and changes from the baseline to final visit will be summarized. Descriptive summary statistics (mean, SD, median, and range) for vital sign data, height, weight, and BMI will be evaluated.

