3.5 Treatment Phase (4 weeks)

3.5.1 Titration Period, Day 1 to Day 14

Subjects will be instructed to titrate to reach the maintenance dose over a period of 15 days, according to the dose titration schedule shown in Figure 1 and Figure 2. Dosing will begin at SPN-810, and increase to on Day 3, 9 mg/day on Day 5, on Day 8, on Day 11, and on Day 15.

3.5.2 Maintenance Period, (14 days) Day 15 to Day 28

Following dose titration, treatment will be maintained for 2 weeks at 36 mg/day SPN-810 or placebo.

At Visit 4, before the end of the Maintenance period, blood will be drawn for quantitative PK analysis. The morning dose of study medication will be administered in the clinic. The following PK samples will be collected: pre-dose (-30 minutes), and 2, 3, 4 and 6 hours post-dose (± 15 minutes).

At Visit 4, all subjects will also have the option to participate in an OLE study (Protocol 810P304) in which all subjects will receive active treatment. At the visit, subjects will receive a blinded conversion medication card that will adjust the subject's total daily dose to 18 mg SPN-810 for initiation into the OLE (Figure 1). Those subjects who do not elect to participate in this extension study will be tapered down prior to discontinuation of the study medication and will receive a taper down card at Visit 4 (Figure 2).

At Visit 5, subjects will return to the Imaging Center for the post-treatment fMRI/PSAP Task and will use (when applicable) the same Caseforge helmet used at Visit 2.

At the completion of the MRI scans (Visit 2 and Visit 5), subjects will be administered the questionnaire to validate their understanding of the task and to describe the characteristics of their opponent. The results of the questionnaire will be provided to the study site.

3.6 Taper/Conversion Phase (7 days), Day 29 to Day 35

Subjects will complete the 1-week Taper or Conversion phase.

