3.7 End of Study (EOS)/Early Termination, Visit 6 (Day 35)

Subjects will return to the study site for a final visit, after completing the 1-week Taper or Conversion phase. Those subjects who choose to continue into the OLE study will have procedures performed for that study; eligibility criteria will be confirmed at Visit 1 of study protocol 810P304. Only the subjects who discontinue from the study during the Maintenance

period or following Day 14 in the Titration period will be offered a Taper card at the study site one week prior the EOS. All subjects who discontinue early (i.e., during the Titration period, Day 1 to Day 14) will be instructed to return to the study site for a final visit (EOS), within 1 week after discontinuation.

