4.2.4 Maintenance/Visit 4 (Day 21)

Visit 4 will occur 21 days after the start of the Titration period. Subjects will be instructed to take their morning dose at the site. The following procedures will be performed:

- 1. Administer CGI-I and CGI-S.
- Administer R-MOAS.
- 3. Record Vital Signs (Heart Rate [HR], Blood Pressure [BP], Temperature, and Respiration Rate [RR]).
- 4. Perform Physical Examination.
- 5. Record Height, Weight, and BMI.
- 6. Perform 12-lead ECG.
- 7. Collect blood samples for PK.
- 8. Administer C-SSRS.

- 9. Administer Safety Scales (Simpson-Angus, Barnes Akathisia Rating, and AIMS).
- 10. Record Adverse Events.
- 11. Record Concomitant Medications.
- 12. Assess Drug Compliance.
- 13. Drug Return.
- 14. Dispense Study Medication (Either Conversion or Taper dose based on subject's decision to participate in OLE.

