4.2.6 Taper/Conversion/Visit 6 (Day 35)/EOS

Visit 6 will occur approximately 7 days (±2 days) following Visit 5 according to the Schedule of Events and Procedures. These procedures will be performed for all subjects who complete the Maintenance period and for those who discontinue early. Subjects who discontinue during the Maintenance period (between Day 15 and 28) will be offered a Taper card and return to the study site to complete Visit 6. Any subject who discontinues during the Titration period (Days 1-14), will be instructed to return to the study site for the final visit, within 1 week after discontinuation.

- Administer R-MOAS.
- 2. Administer CGI-I and CGI-S.
- 3. Perform Physical Examination.
- Perform 12-lead ECG.

- 5. Collect Urine for Pregnancy Test (FOCP only).
- 6. Record Vital Signs (Heart Rate [HR], Blood Pressure [BP], Temperature, and Respiration Rate [RR]).
- 7. Record Height, Weight, and BMI.
- 8. Collect Blood for Hematology and Chemistry.
- 9. Collect Urine for Urinalysis.
- 10. Administer C-SSRS.
- 11. Administer Safety Scales (Simpson-Angus, Barnes Akathisia Rating, AIMS).
- 12. Record Adverse Events.
- 13. Record Concomitant Medications.
- 14. Collect Study Medication and Assess Treatment Compliance.
- 15. Obtain written Informed Consent and Assent for OLE study.
- 16. Complete/Discontinue Subject.

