4 STUDY DESIGN

This is a multi-center, double-blind, randomized (1:1), placebo-controlled, parallel-group, 2-arm study.

The study will screen approximately 40 male and female subjects, aged 8-12 years inclusive, with ADHD and IA, to achieve an approximate enrollment of 30 subjects.

This study consists of 3 phases: Pre-Treatment, Treatment, and Conversion/Taper.

The Pre-Treatment Phase comprises of Screening and a Baseline MRI Visit for a total duration of up to 30 days. Following Screening (Visit 1), eligible subjects will proceed to the Baseline MRI visit (Visit 2) at the Imaging Center, where the brain MRI scans will be performed. At Visit 3, eligible subjects will be randomized to study medication or placebo.

Eligible subjects will follow a dose-titration schedule with initial dosing at approximately every 2 days until the target dose (36 mg/day) is reached. The final dose will be maintained for 2 weeks (Maintenance period) during which time subjects will return for PK sampling (Visit 4) prior to receiving the final MRI scan at the Imaging Center (Visit 5). At the intervening visit during the maintenance phase (Visit 4), subjects will be given the option to taper down/discontinue study medication or convert to an ongoing OLE study (810P304) upon completion of the current study and will receive the blinded taper or the conversion study medication kit. Subjects will return to the study site for a final EOS visit (Visit 6), after completing the 1-week Taper or Conversion phases. Subjects who choose to convert into the ongoing OLE (SPN-810 304) will enter the study at a dose of 18 mg/day SPN-810.

This study is designed to use fMRI in conjunction with the PSAP aggression task. MR imaging parameters for the PSAP Task were optimized in the non-interventional 810P204a study that was conducted by the Sponsor in typically developing children 8-12 years of age.

5 **ANALYSIS VARIABLES**

5.1 **Primary Variables**

The primary analysis variable will be the treatment effect of SPN-810 on the change in BOLD fMRI contrast associated with the aggressive response from Baseline (Visit 2) to Visit 5 measured in subjects with ADHD and IA participating in the PSAP aggression Task.

Briefly, the primary endpoint is the change in brain activity measured by a change in BOLD response in brain regions during provocation or during the aggressive response relative to the monetary response at baseline and following 4 weeks treatment with SPN-810, compared to placebo.

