7.6.4 ECG Results

Tabular summaries of the quantitative ECG parameters and the overall ECG findings (normal, abnormal not clinically significant, or abnormal clinically significant) will be presented. The QT will be corrected using Fridericia's method.

ECG results will be summarized by visit and by treatment group using descriptive statistics (for quantitative ECG parameters) and frequency tables (for qualitative ECG parameters, including the overall ECG finding). For quantitative ECG parameters, both actual values and change from Baseline values will be summarized.

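### SAP 7.6.3 names a change from baseline only at Visit 6, after taper or conversion, and none at Visit 4, the only scheduled on-dose record

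*SAP*

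**What the plan says.** SAP 7.6.3 plans by-visit, by-arm descriptive summaries of vital signs and then adds: "Both actual values and changes from the baseline to final visit will be summarized". A last sentence promises descriptive statistics for vital signs, height, weight and BMI. It mentions neither visits nor change. Protocol 8.3.3 has the same change sentence.

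The final visit is Visit 6. Protocol 3.7 says: "Subjects will return to the study site for a final visit, after completing the 1-week Taper or Conversion phase". Protocol 4.2.6 places it: "Visit 6 will occur approximately 7 days (±2 days) following Visit 5".

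Dosing differs between Visit 4 and Visit 6. At Visit 4 the child is on the maintained randomised dose, and Protocol 4.2.4 adds: "Subjects will be instructed to take their morning dose at the site". For the week before Visit 6, Protocol 3.5.2 says that "all subjects will also have the option to participate in an OLE study (Protocol 810P304) in which all subjects will receive active treatment", and that those who choose it receive a "blinded conversion medication card that will adjust the subject's total daily dose to 18 mg SPN-810". SAP section 4 agrees: "Subjects who choose to convert into the ongoing OLE (SPN-810 304) will enter the study at a dose of 18 mg/day SPN-810". Subjects who decline the extension are tapered.

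**The concern.** A change from baseline is the usual way to show a drug effect on heart rate, blood pressure or weight. Here the one change named is taken when no child is still on the maintained randomised regimen. Subjects from the 36 mg/day arm have tapered or moved to 18 mg/day. Protocol 3.5.2 makes no exception for placebo subjects when it describes the 18 mg conversion card. Similar changes in the two arms at Visit 6 could therefore reflect doses that have moved closer together, and a reader might take them as evidence that the drug has no effect.

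Vital signs are a listed secondary safety endpoint in both documents. Weight and BMI are not listed endpoints, but Protocol 1.6 says that molindone's effect on body composition will be evaluated.

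**Working it through.** The plan gives no figure to reproduce on this point. The check sets the visit schedule, the dosing periods and the SAP wording side by side.

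**Inputs.** Visit days, windows and procedures are from Protocol Table 1 and 4.2.4 to 4.2.6. Dosing periods are from Protocol 3.5 and 3.6: 36 mg/day or placebo on Days 15 to 28, taper or conversion on Days 29 to 35.

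**Timing.**
- Visit 4 is Day 21 with a window of −2/+1 days: 21 − 2 = 19 and 21 + 1 = 22, so Day 19 to 22. This lies inside Days 15 to 28.
- Days at 36 mg by Visit 4, counting Day 15 as the first: 19 − 15 + 1 = 5, 21 − 15 + 1 = 7 and 22 − 15 + 1 = 8.
- Visit 5 is Day 28 ± 1, so Day 27 to 29.
- Visit 6 is 7 ± 2 days after Visit 5, so 5 to 9 days after it: 27 + 5 = 32 and 29 + 9 = 38, so Day 32 to 38. All of this is after Day 28.

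| Visit | Day | Treatment at that time | Vital signs, height, weight, BMI scheduled? | Change named in SAP 7.6.3? |
|---|---|---|---|---|
| 1 | Screening | None | Yes | Reference |
| 4 | 19–22 | 36 mg/day or placebo | Yes | No |
| 5 | 27–29 | 36 mg/day or placebo | No (imaging and a follow-up call) | – |
| 6 | 32–38 | Taper or conversion | Yes | Yes |

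**Count.** Scheduled post-baseline records on the maintained randomised dose: 1 (Visit 4). Changes named: 1 (Visit 6). Changes named at Visit 4: 0.

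**Height, weight and BMI.** The change sentence follows a sentence about vital signs. If the section heading extends it to height, weight and BMI, their only planned change is at Visit 6. If it does not, no change is planned for them. The text does not settle which.

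**Comparison within the SAP.**
- SAP 7.6.7 names change at both Visit 4 and Visit 6 for the movement scales.
- SAP 7.6.4 covers ECG, recorded at the same three visits. It plans by-visit summaries and adds, without limiting change to the last visit: "For quantitative ECG parameters, both actual values and change from Baseline values will be summarized".
- SAP 7.3 and 7.6.1 present exposure and adverse events for titration, maintenance and the two combined. The vital-sign change falls outside all of these periods.

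**The case against.** **The wording may mean a span of visits.** After a by-visit sentence, baseline to final visit could mean every visit through the last, which would include change at Visit 4. This is possible but is not the plain reading, because SAP 7.6.7 names Visit 4 where it is meant. If the span was intended, the proposed wording makes it clear.

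**The information is not lost.** This stands. Visit 4 vital signs by arm are planned, so an on-dose difference that faded by Visit 6 would show in the same output. SAP 6.1 also promises subject listings, from which each child's change, and its mean and SD, can be computed. A reader might infer that the on-dose change cannot be recovered. The documents do not support that: what is missing is a planned summary.

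**Visit 6 is a reasonable time for weight.** This stands in part. Visit 4 comes after only about 5 to 8 days at 36 mg, and Visit 6 gives the only scheduled weight after the full 28 days. That is a reason to show both visits.

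**Visit 4 is not the only possible record.** This is correct. Protocol 4.2 allows unscheduled visits, and Protocol 6.3.5 allows vital signs at any other time. The statement holds for scheduled records only.

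**Conclusion.** The point holds as a cheap improvement. On its plain reading, SAP 7.6.3 plans one change from baseline, at a visit after the randomised regimen has ended. It plans none at the only scheduled on-dose visit, and it leaves change in height, weight and BMI unclear.

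The impact is small. SAP 6.1 says that the study ended early and that all analyses are descriptive, so no test depends on this, and the on-dose change can be recovered.

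A reader might go further and put a size on the dose convergence at Visit 6, or conclude that the arms would then be indistinguishable. The documents do not support either. The day-by-day taper and conversion schedule is in a figure that is not shown, no conversion rates are given, and dose is not linked to any change in a vital sign or in weight. Weight and BMI also build up over time, so a dose change in the last week would blur them only in part.

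The conclusion rests on taking the final visit to be Visit 6, as Protocol 3.7 and SAP section 4 both do, and on Table 1 as the schedule of measurements.

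**What to change.** In SAP 7.6.3, replace the change sentence with:

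*Actual values and changes from baseline (Visit 1) in vital signs, height, weight and BMI will be summarized by treatment group at Visit 4 (on randomized dose) and at Visit 6 (after taper or conversion).*

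Flag subjects who converted in the listing. A tabulated split by conversion is not needed, because cells could be very small in a study that ended early.

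The cost is one sentence and a few table rows. Nothing new is collected, since all four measures are already scheduled at Visits 1, 4 and 6. The downside is that Visit 4 is early for weight, so Visit 6 must be kept beside it.

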7.6.4 ECG Results

Tabular summaries of the quantitative ECG parameters and the overall ECG findings (normal, abnormal not clinically significant, or abnormal clinically significant) will be presented. The QT will be corrected using Fridericia's method.

ECG results will be summarized by visit and by treatment group using descriptive statistics (for quantitative ECG parameters) and frequency tables (for qualitative ECG parameters, including the overall ECG finding). For quantitative ECG parameters, both actual values and change from Baseline values will be summarized.

7.6.5 Physical Examinations

Findings from the physical examinations will be listed for each system or area examined.

7.6.6 *C-SSRS*

C-SSRS outcomes will be summarized using number and percent of subjects by categories for suicidal ideation only, suicidal behavior only, and suicidality (ideation and behavior combined). The summary will be presented by treatment group.

7.6.7 Extrapyramidal Symptoms

The occurrence of neurological side effects will be assessed by examining the observed score at each visit and change from baseline at each post-baseline (Visit 4 and Visit 6) for the Simpson-Angus Scale, Barnes Akathisia Rating Scale, and AIMS.

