8.3.8 Extrapyramidal Symptoms

The occurrence of neurological side effects will be assessed by looking at the changes in scores from Baseline to Visit 4 and Visit 6 for each of the Simpson-Angus Scale, Barnes Akathisia Rating Scale, and AIMS. For each item on each of these scales, the number (and percentage) of subjects with a worse score at any post-Baseline visit, compared to Baseline, will be presented. A listing of these subjects will also be provided.

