1 INTRODUCTION

The purpose of this statistical analysis plan (SAP) is to ensure the credibility of the study findings by specifying the statistical approaches to the analysis of the data. This SAP covers the planned analyses of all data collected on the eCRFs, and will identify handling of data issues. The statistical analysis plan presented in this document will supersede the statistical analysis methods described in the clinical protocol. Any deviations/changes from the planned analyses described in this SAP will be identified, with justification, in the appropriate section of the clinical study report. This SAP is based on the clinical study protocol 810P204, version 3.0, dated 12 Apr 2019 and its associated electronic case report forms (eCRF).

2 **STUDY OBJECTIVES**

The primary objective is to evaluate the effect of SPN-810 treatment on brain activity in subjects aged 8-12 years with ADHD and IA using functional Magnetic Resonance Imaging (fMRI).

Secondary objectives are to evaluate the effect of SPN-810 treatment on:

- The functional connectivity between brain regions using resting-state fMRI (rs-fMRI)
- The concentration of neurotransmitters glutamate and gamma-aminobutyric acid (GABA) using Magnetic Resonance Spectroscopy (MRS)
- Safety of SPN-810

Tertiary objectives are to evaluate the following:

- Pharmacokinetics (PK) of Molindone
- Effect of SPN-810 treatment on the Clinical Global Impression-Severity (CGI-S) and -Improvement (CGI-I) scores
- Effect of SPN-810 on the Retrospective-Modified Overt Aggression Scale (R-MOAS) score.

3 **ENDPOINTS**

Primary Endpoint is the change in the whole brain in BOLD fMRI contrast in response to the PSAP task from Baseline (Visit 2) to Visit 5.

Secondary Endpoints are:

- Change in functional connectivity as reflected in the Fisher's Z-transformation of correlation coefficients between brain regions during rs-fMRI from Baseline (Visit 2) to Visit 5.
- Change in the concentrations of neurotransmitters GABA and glutamate in the anterior cingulate cortex (ACC) from Baseline (Visit 2) to Visit 5 as determined by MR spectroscopy.
- Safety endpoints:
 - 1) Adverse events.
 - 2) Safety scales (Simpson-Angus Scale, Barnes Akathisia Rating Scale [BARS], and Abnormal Involuntary Movement Scale [AIMS]).
 - 3) Clinical laboratory tests (hematology, chemistry, and urinalysis).

- 4) Vital signs.
- 5) Electrocardiograms (ECGs).
- 6) Columbia-Suicide Severity Rating Scale (C-SSRS).

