6 STATISTICAL METHODS

6.1 General Notions

The primary and secondary endpoint data (Section 7.4 and 7.5) were handled and analyzed by [name]., Department of Radiology, Northwestern University, Chicago, IL 60611. All other data were analyzed at Supernus using SAS version 9.

Tabular summaries of the data collected during the study will provide a general description of the subjects studied and an overview on brain functioning, GABA and Glu levels, and safety results by study treatment group. Due to early termination of the study, all statistical analyses will be descriptive without any hypothesis testing. Continuous variables will be summarized using descriptive statistics [number of subjects, mean, standard deviation (SD), median, and minimum and maximum]. Categorical (nominal) variables will be summarized by reporting the frequency and percentage of subjects in each category.

In addition, subject data listings, as specified in Sections 16.2 and 16.4 of ICH Guidance E3, will be provided. Analysis processing will be performed before the database is released. Any deviation from the statistical plan will be documented and described in the final report.

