7.5.2 GABA and Glutamate Concentrations

The concentrations of GABA and Glu in the ACC will be obtained during MRS acquisition. The descriptive analyses will be used to examine the concentrations of GABA and Glu by treatment group and visit (pretreatment at Visit 2 fMRI scan and post-treatment at Visit 5). The change from baseline (Visit 5 – Visit 2) in concentration of GABA and Glu will also be assessed for each treatment group.

7.6 **Safety Analysis**

Evaluation of safety will be performed for the safety population. Safety data that will be evaluated include AEs, clinical laboratory results, vital signs, ECGs, and findings from the physical examinations. The occurrence of neurological side effects will be assessed by looking at any worsening in scores from Visit 1 to the end of the study visit for each of the Simpson-Angus Scale, Barnes Akathisia Rating Scale, and AIMS. Suicidal ideation and suicidal behavior will be measured by the C-SSRS.

All summary tables related to safety analyses will use the safety population.

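### SAP 7.6.7 drops, without a stated reason, the protocol's count and listing of children whose extrapyramidal scale scores worsened

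*SAP*

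**What the plan says.** Protocol 8.3.8 plans three outputs for the Simpson-Angus Scale, BARS and AIMS:

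- Side effects are to be "assessed by looking at the changes in scores from Baseline to Visit 4 and Visit 6".
- For each item of each scale, "the number (and percentage) of subjects with a worse score at any post-Baseline visit, compared to Baseline, will be presented".
- Third comes detail on the individual children: "A listing of these subjects will also be provided".

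SAP 7.6.7 keeps the first, adding the observed scores: occurrence is to be "assessed by examining the observed score at each visit and change from baseline at each post-baseline (Visit 4 and Visit 6". It does not mention the second or the third. SAP 7.6 has a general sentence, also found in Protocol 8.3, that side effects are to be "assessed by looking at any worsening in scores from Visit 1 to the end of the study visit". It defines no count, percentage, item level or table.

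Two statements govern how these fit together. SAP 1 says that the SAP "will supersede the statistical analysis methods described in the clinical protocol". SAP 6.1 says: "Due to early termination of the study, all statistical analyses will be descriptive without any hypothesis testing".

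**The concern.** SAP 7.6.7 sets out to assess the occurrence of neurological side effects. Occurrence is a matter of how many children were affected in each arm, and the output that answered it has been removed. Because the SAP takes precedence, the protocol's table cannot be assumed to survive.

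Protocol 3.1 says that these scales were chosen specifically to monitor extrapyramidal symptoms, since youths on antipsychotics are at greater risk than adults. SAP 3 lists them among the safety endpoints. At stake is whether the report states, by arm, what share of children worsened on a scale item at any visit after baseline.

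**Working it through.** The documents give no extrapyramidal rate or target for these scales, so there is no figure to reproduce. The check compares the texts and then asks whether the retained statistics could yield the dropped count.

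**1. Does early termination explain the omission?** SAP 6.1 removes hypothesis testing and keeps description. The SAP's treatment of other safety data shows how that works:

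- C-SSRS: Protocol 8.3.7 planned number and percent plus a Fisher or chi-square comparison. SAP 7.6.6 drops the test and keeps number and percent.
- Laboratory values: SAP 7.6.2 keeps the shift tables.
- Extrapyramidal scales: Protocol 8.3.8 planned no test, only a count and a listing. SAP 7.6.7 drops both.

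A count with a percentage is descriptive, so the stated reason does not reach it.

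**2. Can the count be recovered from the summaries?** The inputs are the continuous-variable statistics in SAP 6.1 (n, mean, SD, median, minimum, maximum) and the planned 15 per arm (Protocol 4.1). The individual changes below are assumed for illustration; a positive change means worse. Mean = sum of changes / n.

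- Two children worsen by 3, six improve by 1, seven are unchanged: mean = (2×3 − 6×1)/15 = 0.00, SD 1.31, median 0, minimum −1, maximum 3. Worsened: 2/15 = 13.3%.
- One child worsens by 3, seven improve by 1, seven are unchanged: mean = (3 − 7)/15 = −0.27, median 0. Worsened: 1/15 = 6.7%.
- Arm A has changes of 3, 1, 1, 1, eight zeros and three of −1. Arm B has 3, 1, twelve zeros and one of −1. Means: A = (3 + 3 − 3)/15 = 0.20; B = (3 + 1 − 1)/15 = 0.20. Both have median 0, minimum −1 and maximum 3. The SDs are 1.01 and 0.86. Worsened: A 4/15 = 26.7%, B 2/15 = 13.3%.

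The mean, median, minimum and maximum therefore do not determine the count. The SD differs between A and B but cannot be converted into a count.

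**3. Can the any-visit count be recovered from visit-by-visit summaries?** Suppose two children worsen by 3 at Visit 4 only and two others by 3 at Visit 6 only, with no other changes. Each visit shows mean = 6/15 = 0.40, median 0 and 2/15 worsened. The protocol's any-visit count is 4/15 = 26.7%. Even a count at each visit would not give it.

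**4. Smaller arms.** The SAP gives no achieved sample size, so n = 10 and n = 6 were also tried, with one or two children worsening by 3 and the others unchanged or about half of them improving by 1. The median change is 0 in every case, while 10.0% to 20.0% (n = 10) or 16.7% to 33.3% (n = 6) worsened.

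**5. Which visits carry the scales?** By Protocol 4.2.4 to 4.2.6, they are given at Visit 4 (Day 21, in the maintenance period) and Visit 6 (Day 35, after the one-week taper or conversion), and not at Visit 5. Visit 4 is thus the only scheduled scale visit at the target dose. SAP 7.6 does not name it.

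**6. Is there a baseline?** Protocol 6.3.9.1 to 6.3.9.3 place all three scales at Visit 1. The Visit 1 procedure list in Protocol 4.2.1 omits them, and the safety-scale row of Table 1, as extracted, shows marks only at Visits 4 and 6. The dropped count and the retained change scores both need that baseline.

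**The case against.** A reader might infer that the SAP substitutes a new method for the protocol's, and that emergent extrapyramidal symptoms in a few children could be averaged away and reported as no signal. The documents do not support either inference.

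- Protocol 8.3.8 already contained the change-from-baseline summaries. The SAP omits a component rather than replacing the method.
- Protocol 6.3.3 separates a positive scale finding from an extrapyramidal event. Events judged to be adverse events are tabulated under SAP 7.6.1 by arm, by period, by highest severity and by dose at first occurrence. Protocol 6.3.2.2 also requires 24-hour reporting and a running incidence summary.
- A positive maximum change shows that at least one child worsened. SAP 6.1 keeps the general ICH E3 subject listings, and with about 30 planned subjects individual scores could be read from listings of that kind.
- SAP 7.6 can be read as covering any worsening over the whole span from Visit 1 to the last visit. Protocol 8.3 uses the same sentence alongside the any-visit count in 8.3.8. It cannot be said that a child who worsened at Visit 4 and then recovered would necessarily be missed.
- SAP 7.6.7 does not say whether it means items or totals, or whether scores are treated as continuous or categorical. If categorical, SAP 6.1 would give frequencies of observed scores.
- The data sets above are constructed.

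All of this stands, and it limits the point. It does not restore the output. Because a worse score need not become an adverse event, the TEAE tables do not stand in for the scale count. General listings leave readers to derive the rate by arm themselves. Frequencies of observed scores at each visit do not identify who worsened from baseline. On either reading, SAP 7.6 defines no table.

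**Conclusion.** The point holds as an unexplained omission from the safety reporting. The per-item number and percentage of children worse at any post-baseline visit, and the listing of those children, are gone, and what remains does not reproduce them. The loss is the scale-based rate by arm, not all sight of extrapyramidal symptoms.

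Its actual size cannot be stated, because the documents give neither scale results nor the achieved sample size. The illustration shows that a twofold difference in the count (4 against 2 of 15) can sit behind the same mean, median, minimum and maximum. This assumes that scores are summarized as continuous variables and that arms are of the planned size. The textual omission depends on neither assumption. Whether worsening or change can be calculated at all depends on a Visit 1 assessment that the protocol does not describe consistently.

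**What to change.** In SAP 7.6.7, reinstate the Protocol 8.3.8 table: by arm and item, n (%) of subjects with a worse score than baseline at any post-baseline visit, with the listing of those subjects. Keep the observed-score and change summaries as supportive, and make the worsening sentence in SAP 7.6 refer to this rule. A separate Visit 4 column would be useful but is optional; the protocol did not plan one. If the sponsor prefers to omit the count, the SAP should say so and justify it.

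Before that, reconcile Protocol 6.3.9.1 to 6.3.9.3 with Table 1 and section 4.2.1, and confirm whether baseline scores exist. If none were taken, report n (%) by observed score category at Visits 4 and 6, and state that neither change nor worsening can be derived.

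The cost is SAP wording, one table and one listing, with no new patients or procedures, provided the baseline is confirmed.
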